## **14.0 BIOSTATISTICS**

The primary objective of this study is to determine the 2-year loco-regional progression-free rate. Current literature showed that the 2-year loco-regional progression-free rate is about 40% [16-24]. We expect to improve this rate substantially to 90% by applying the proposed chemoradiation treatment strategy. It should be mentioned that according to previous versions of the protocol 8 patients had been treated with IMRT alone. But prospectively we will treat patients with the current standard which is chemoradiation. To this end we will still employ a single-stage binomial design. We will recruit 19 patients, and we will claim the proposed treatment promising when at least 14 patients are without progression of disease at 2 years from the end of the treatment. This decision rule gives a power (that is, probability of declaring success when the true 2-year progression rate is 90% or higher) of 0.99 with the

type 1 error rate (that is, probability of declaring success when the true 2-year progression rate is 40% or lower) less than 0.01. Patients who died due to any reason, or were lost to F/U within 2 years will be regarded as having loco-regional progression. Patients who do not complete treatment due to excessive toxicity will be excluded from the primary endpoint analysis and replaced by new eligible patients. We expect to accrue the total of 19 analyzable patients in 2 years. The 8 patients who had received IMRT alone will not be counted towards this endpoint and will be summarized separately.

To better understand the loco-regional progression we will also use the cumulative incidence function for summaring the endpoint of time to loco-regional failure, which will be carried out by a competing risks anlaysis. Overall survival rates will be assessed by Kaplan-Meier method. Rates of (acute or late) toxicities will be computed by sample proportions and confidence intervals will also be provided. Summary statistics and/or longitudinal plots for the Modified Barium Swallow-Imp and Penetration-Aspiration scales will be supplied for assessing objective measures of late dysphagia. BRAF and other mutation measurements at baseline will be correlated with clinical outcomes such as overall survival and local-regional control using survival analysis tools. All secondary endpoints will be analyzed for the 19 patients under chemoradiation. The 8 patients who had received IMRT alone will be summarized separately.

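### A toxic death before the end of treatment falls under two Section 14 rules, failure and exclusion with replacement, and nothing says which prevails

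*Combined protocol and SAP*

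**What the plan says.** Section 14.0 (Biostatistics) sets a single-arm test on 19 patients. Its decision rule reads: "claim the proposed treatment promising when at least 14 patients are without progression of disease at 2 years from the end of the treatment". The null rate is 40% and the target 90%, with stated power 0.99 and type I error below 0.01.

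Two adjacent sentences then deal with patients who do not reach the 2-year assessment in the ordinary way. The first scores deaths and losses as failures: "Patients who died due to any reason, or were lost to F/U within 2 years will be regarded as having loco-regional progression". The second takes a separate group, those stopped by toxicity, out of the analysis: "Patients who do not complete treatment due to excessive toxicity will be excluded from the primary endpoint analysis and replaced by new eligible patients". The sentence after that refers to the analysable number: "We expect to accrue the total of 19 analyzable patients in 2 years".

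Section 13.0 (Criteria for Removal from Study) takes a different line. A patient with unacceptable toxicity leaves the study and counts as a treatment failure, and every enrolled patient enters an intent-to-treat analysis. Section 13.0 also allows a patient who cannot receive doxorubicin because of its toxicity to stay on study and continue IMRT. Section 12.0 defines loco-regional failure by imaging and does not mention death.

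**The concern.** Neither Section 14 sentence carves out an exception for the other. A patient killed by toxicity during chemoradiation has died of a cause covered by the first sentence and has failed to complete treatment for the reason named in the second. Under the first, the patient is one of the 19 and a failure. Under the second, the patient is not among the 19, and a newly enrolled patient has a fresh chance of success.

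The case left open is the worst outcome the treatment can produce, in a protocol whose summary says it exists to capture toxicity prospectively. The trial is single-arm and toxicity is known as it happens, so without a written rule the classification would be made after the event, by people who know it. The replacement reading can only favour a positive verdict.

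**Working it through.** **Inputs.** From Section 14.0: n = 19, success threshold 14, null rate 0.40, target rate 0.90. Assumption: exactly one patient dies of toxicity before completing treatment. The documents give no rate for this. The true rates 0.70 and 0.80 are illustrative intermediate values that the plan does not use.

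**Step 1: reproduce the plan's own figures.** With X the number progression-free at 2 years among 19:

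- Power = P(X ≥ 14 | n = 19, p = 0.90) = 0.9914 (stated 0.99).
- Type I error = P(X ≥ 14 | n = 19, p = 0.40) = 0.0031 (stated below 0.01).

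The design arithmetic is right for 19 analysable patients.

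**Step 2: one toxic death, two readings.**

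- Scored as failure: that patient is one of the 19, so 14 successes must come from the other 18. The chance of a claim is P(X ≥ 14 | n = 18, p).
- Excluded and replaced: there are still 19 analysable patients. The chance of a claim is P(X ≥ 14 | n = 19, p).

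| True rate p among the other patients | Scored as failure | Excluded and replaced | Difference |
|---|---|---|---|
| 0.40 (null) | 0.0013 | 0.0031 | 0.0018 |
| 0.70 | 0.333 | 0.474 | 0.141 |
| 0.80 | 0.716 | 0.837 | 0.121 |
| 0.90 (target) | 0.972 | 0.991 | 0.020 |

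The differences are taken before rounding. Each equals p × P(X = 13 | n = 18, p): the verdict changes only when the other 18 give exactly 13 successes and the replacement also succeeds. At p = 0.70 this is 0.70 × 0.2017 = 0.141, which agrees with the table.

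**Step 3: the borderline case in counts.** Suppose the first 19 patients give 13 successes, 5 ordinary failures and 1 toxic death.

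- Death scored as failure: 13/19, below the threshold.
- Death replaced and the replacement succeeds: 14/19, threshold met. Twenty patients were treated, and 14/20 = 70%.

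**Step 4: does Section 13 settle it?** Its treatment-failure and intent-to-treat wording points to failure without replacement. Section 14 excludes and replaces. The two sections disagree for anyone whose toxicity both ends treatment and counts as unacceptable, so Section 13 cannot be used to interpret Section 14 until they are reconciled.

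**The case against.** The best reply is that the two sentences do different jobs. One scores outcomes and the other defines who is analysed. Exclusion is not a score, and the reference to 19 analysable patients suggests that the set is formed first and outcomes are scored within it. This is a plausible reading, and it makes the problem an unstated precedence more than a flat contradiction. But the text does not say so, and the death rule covers any cause without exception. The reading also drops treatment-caused deaths from the primary result, contrary to the sense of Section 13.

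It could also be said that the 2-year clock starts at the end of treatment, so an on-treatment death comes before it. The death sentence names no starting point, and a patient who died on treatment cannot be progression-free 2 years later.

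A third reply is that the event may be rare. The retrospective series in Section 3.0 reports grade 3 toxicities and mentions no treatment-related death, doxorubicin is described as low dose, and patients may continue IMRT without it. This stands: one such patient is an assumption, not a forecast.

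A reader might infer a much wider overlap, in which patients who stop alive for toxicity and die or are lost later also meet both rules. Mortality in that series is substantial (3-year survival 54.4%), which makes the inference tempting. The documents do not support it. Such a patient is excluded and replaced on stopping, and nothing suggests that a later death brings the patient back. The series is also retrospective, with 21 of 66 patients given concurrent chemotherapy, and no rate of stopping for toxicity is given.

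**Conclusion.** The point holds for a narrow group: patients who die of toxicity before completing treatment. Section 14 gives them two incompatible dispositions without an order. One of the two removes treatment-caused deaths from the decision rule, which biases the result towards success and conflicts with Section 13.

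Under the assumption of one such patient, the choice hardly matters at the design rates: type I error is below 0.01 and power above 0.97 either way. At true rates of 0.70 to 0.80 it moves the chance of a positive claim by 12 to 14 percentage points, and it can decide a borderline result. A reader might infer that the stated power and type I error are wrong. They are not; both reproduce. What is missing is a rule saying which patients they apply to. This should be fixed, but it does not undermine the design.

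**What to change.** Make two changes, both to endpoint scoring only. No dose, schedule or clinical rule is affected.

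1. In Section 14, state that a death from any cause before treatment is completed, toxic death included, counts as a failure in the 14-of-19 analysis and is not replaced.
2. Reconcile the exclude-and-replace sentence with Section 13's failure and intent-to-treat wording, so that a patient who stops alive for toxicity has one stated classification. The one consistent with Section 13 is failure, not replaced. Say also whether stopping doxorubicin alone while continuing IMRT counts as completing treatment for this purpose.

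**Cost.** A few sentences across two sections, a slightly lower observed success rate if such events occur, and some power. With one toxic death and a true rate of 0.90 in the others, power is 0.972 instead of 0.991.

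The second change reaches more patients and may cost more. If a share t of all patients fails to complete for toxicity and the rest succeed at 0.90, the success rate becomes 0.90 × (1 − t). The documents give no t. For an assumed 5%, that is 0.855, with power 0.953; for 10%, it is 0.81, with power 0.864. The sponsor should check that it accepts this loss.

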# 1.0 PROTOCOL SUMMARY AND/OR SCHEMA

This is a single-institution, non-randomized, phase II study. The primary endpoint is to determine the 2-year loco-regional progression-free interval for non-anaplastic and non-medullary thyroid cancer patients with unresectable disease or gross residual disease after surgical resection treated with definitive IMRT. Eligible patients will be enrolled and will receive standard definitive IMRT to 70Gy in once-daily fractions with concurrent weekly doxorubicin (10 mg/m^2). This is a standard of care protocol to capture acute and late toxicities prospectively.

All patients will undergo baseline history and physical exam, laboratory studies and biopsy as part of the initial assessment for protocol eligibility. Baseline imaging will include FDG PET/CT scan, according to our standard of care. Standard FDG PET/CT can be done prior to radiation simulation or can be incorporated as part of the standard FDG PET/CT radiation simulation. Recommended approximate weekly DW and multiparametric MRI will be available to both Main Campus and regional patients unless contraindicated. Research multiparametric MR scans for both Main Campus and regional patients will be performed on the same designated Philips 3T scanner located in the Main Hospital in the Department of Radiation Oncology team utilize modern fusion soft wares that allows for the fusion of anatomy with or without the use of immobilization devices during research MRI scans. As fusion soft wares help ensure patients' are in the same position, patients are allow to undergo optional research MRI's without utilizing immobilization devices. DWI-MR images will also be acquired according to the standard IVIM departmental protocol when available. Patients will be seen weekly during radiation as per standard procedure at MSKCC.

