## Secondary Objectives:

- **2.2.1** To determine the overall survival rates
- 2.2.2 To evaluate the rates of acute toxicities (CTCAE, v. 4) during treatment
- 2.2.3 To evaluate the rates of late dysphagia, dry mouth, and other toxicities (CTCAE, v. 4)

- **2.2.4** To assess objective measures of late dysphagia using standard Modified Barium Swallow-Imp and Penetration-Aspiration scale (pre-treatment, 6 months, 12, months, 18 months, and 24 months post-treatment.
- **2.2.5** To evaluate BRAF and other exploratory mutations at baseline and correlate with treatment outcome.
- **2.2.6** To assess changes in tumor heterogeneity over the course of external beam RT using serial multiparametric MR scans
- **2.2.7** To assess normal tissue response as a function of dose for parotid, submandibular glands, muscles and bones in the head and neck region during and after EBRT using serial multiparametric MR scans

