A retrospective review of 66 patients with gross residual or unresectable non-anaplastic nonmedullary thyroid cancer that underwent EBRT with or without low dose concurrent chemotherapy at Memorial Sloan-Kettering Cancer Center showed that the 3-year locoregional progression-free survival rate was 77.3%, with a 3-year overall survival rate of 54.4%. [51]. The median radiation dose was 6630 cGy (Interguartile range 6000-7000cGy). Concurrent low dose radiation sensitizing chemotherapy was administered to 21 of the 66 patients (31.8%) with a non-significant increase in the 3-year locoregional progression-free survival rate (90.0% versus 73.0%). Despite this improvement in local control, there was no difference in the median overall survival (43.1 versus 37.1 months) likely secondary to the fact that patients treated with concurrent chemotherapy had larger volume of disease and a greater incidence of poorly differentiated histology both of which are known negative prognostic factors. These promising results were in a heterogeneous cohort of patients with multiple poor prognostic risk factors, majority of whom had RAI refractory disease. This is the only published series focused on patients with gross residual or unresectable disease. Grade 3 acute mucositis and dysphagia occurred in 11 (16.7 %) and 13 (19.7 %) patients, respectively. The addition of concurrent chemotherapy only resulted in a 10% increase in acute grade 3 hoarseness (10% versus 0%), with no differences in acute or late toxicities for dermatitis, dysphagia, mucositis, nausea, vomiting, fatigue, or need for a reactive feeding tube. Late adverse toxicity was notable for percutaneous endoscopic gastrostomy tube use in 4 patients (6.1 %), though 2 of these patients had the percutaneous endoscopic gastrostomy tube placed prior to EBRT. There was no difference in the late toxicities between EBRT and CCRT patients including hoarseness and need for a feeding tube. Although patients with metastatic disease fared worse than patients with localized thyroid cancer, loco-regional control was still achieved in a significant number of patients (61.4% versus 88.4%). Thus, EBRT should be considered, even for patients with metastatic disease, because progression in the thyroid bed or neck can cause significant morbidity. Thus our update of the MSKCC experience demonstrated that in patients with unresectable disease or gross residual disease, the 3 year locoregional progression-free interval was 73.0% in patients treated with EBRT alone and 90.0% in patients who underwent concurrent low dose radiation sensitizing chemotherapy with only a slight increase in hoarseness that was self resolving.

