#### 11.1 Radiation Therapy-Associated Adverse Events

Reversible radioepithelitis of pharyngeal mucosa is expected and its timing with dose and severity will be noted and graded according to NCI CTCAE v4.0. Epilation of treated areas and various degrees of skin reaction are expected. Other expected acute reactions include hypogeusia, dysphagia, thick saliva, hoarseness, radiation dermatitis, nausea, vomiting, anemia, fatigue, and weight loss.

Late toxicities are those that occur at least 3 to 4 months post radiation. Late effects may include permanent xerostomia, hypogeusia, dysphagia, ototoxicity, nasal dryness, serous otitis media, dental decay, hypothyroidism, dysphagia, and trismus. Osteoradionecrosis may occur in 5% or less of patients, but can be reduced by dental evaluation before radiation.

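### Late toxicity is planned as a crude proportion with no time point or rule for incomplete follow-up, and the denominator for all toxicity rates is left unclear after toxicity stoppers are replaced

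*Combined protocol and SAP*

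**What the plan says.** Section 1.0 gives toxicity a central place: "This is a standard of care protocol to capture acute and late toxicities prospectively". Secondary objective 2.2.3 is "To evaluate the rates of late dysphagia, dry mouth, and other toxicities (CTCAE, v. 4"). Section 11.1 fixes the earliest time for a late effect: "Late toxicities are those that occur at least 3 to 4 months post radiation".

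The whole analysis plan for toxicity is one sentence in Section 14.0: "Rates of (acute or late) toxicities will be computed by sample proportions and confidence intervals will also be provided". It gives no time horizon, no denominator, and no rule for patients who die, are lost or leave the study. The same section plans a competing-risks cumulative incidence for loco-regional failure and Kaplan-Meier for survival.

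On the population, Section 14.0 says "All secondary endpoints will be analyzed for the 19 patients under chemoradiation". It also says "Patients who do not complete treatment due to excessive toxicity will be excluded from the primary endpoint analysis and replaced by new eligible patients", and then "We expect to accrue the total of 19 analyzable patients in 2 years".

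Three other provisions bear on the point:
- Section 13.0 takes patients with progressive disease off study, although distant metastases do not end protocol therapy. It also allows removal for persistent non-compliance with follow-up.
- Section 13.0 also promises an intention-to-treat analysis of all enrolled patients.
- Section 10.2.1 keeps patients removed for toxicity on the same surveillance schedule, toxicity grading included, as long as they stay in follow-up.

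**The concern.** There are two separate problems.

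**Estimator.** A crude proportion estimates the probability of late toxicity by two years only if everyone is observed for two years or until death. This plan expects otherwise. It has a loss-to-follow-up rule, but for the primary endpoint only. It takes progressors off study without saying whether their later toxicity data count. If the denominator is 19, a patient who leaves at month 5 is scored as never having a late effect.

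**Denominator.** The 19 patients named for secondary endpoints match the 19 analyzable patients who remain after toxicity stoppers are replaced. Read that way, some of the patients most likely to have had a severe event drop out of the toxicity rates, which is selection on the outcome.

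Patients and clinicians would use these rates to judge the regimen's burden. The confidence interval would not reveal either bias.

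**Working it through.** **The plan's own figure.** Section 14.0 gives no target, precision or denominator for late toxicity, so there is nothing to reproduce for it. The only design calculation is the rule of at least 14 of 19. Exact binomial gives power 0.991 at 90% and type I error 0.003 at 40%, which agrees with the stated 0.99 and less than 0.01.

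**Inputs from Section 3.0 (the institution's 66-patient series).** Three-year overall survival is 54.4%. The three-year loco-regional progression-free rate is 77.3% overall and 90.0% with concurrent chemotherapy. Since 77.3% exceeds the survival rate, these rates cannot count deaths as events, so progression can be given its own hazard.

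**Assumptions, because the documents give no figures.** All hazards are constant and independent. Late toxicity arises only between month 4 and month 24, with a net two-year risk R. One scenario adds loss of 10% a year.

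**Hazards per year.**
- Death: d = -ln(0.544)/3 = 0.203
- Progression: g = -ln(0.900)/3 = 0.035, or -ln(0.773)/3 = 0.086
- Loss: c = -ln(0.90) = 0.105
- Late toxicity for R = 30%: h = -ln(0.70)/(20/12) = 0.214

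**Attrition.** Survival is exp(-d/3) = 93.5% at 4 months and exp(-2d) = 66.6% at two years, or 12.7 of 19. If progression also ends grading, 11.8 (90.0% input) or 10.7 (77.3% input) of 19 are still observed at two years. With the assumed loss added to the 77.3% input, it is 8.6.

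**Formula.** With total exit hazard a, the expected proportion with an observed event is

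h/(a+h) × exp(-a × 4/12) × [1 - exp(-(a+h) × 20/12)].

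Setting a = d gives the cumulative incidence with death competing. For R = 30% this is 0.513 × 0.935 × 0.501 = 0.240. Setting a = d+g, or a = d+g+c, gives the crude rate over 19 when those exits also stop observation.

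| Assumed net risk R | Cumulative incidence, death competing | Crude/19, deaths only | Crude/19, progression ends grading (90.0% / 77.3% input) | Crude/19, 77.3% input plus 10% loss a year |
|---|---|---|---|---|
| 10% | 8.0% | 8.0% | 7.7% / 7.2% | 6.5% |
| 20% | 16.0% | 16.0% | 15.4% / 14.5% | 13.0% |
| 30% | 24.0% | 24.0% | 23.1% / 21.9% | 19.7% |
| 40% | 32.2% | 32.2% | 31.0% / 29.4% | 26.4% |

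At R = 30% the shortfall is 0.9 to 2.1 points from progression, and 4.3 points with the added loss.

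**If the denominator is instead the patients still observed at two years**, with all observed events kept in the numerator, the same illustration gives 0.240/0.666 = 36% (deaths only) up to 0.197/0.455 = 43% (progression and loss). The direction reverses.

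**Replacement (illustrative counts).** Suppose 4 of the 19 retained patients have the event and two toxicity stoppers were replaced.
- Stoppers left out: 4/19 = 21.1%
- Stoppers included, both with the event: 6/21 = 28.6%
- Stoppers included, neither with the event: 4/21 = 19.0%

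For acute toxicity the second line is the more natural case, because these patients stopped because of toxicity during treatment. For late toxicity either is possible.

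**The case against.** The strongest case against runs as follows, and much of it stands.

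- **Death.** A reader might infer from the poor survival in Section 3.0 that deaths push the late rate down. Against a cumulative incidence with death competing they do not: a patient who dies without late toxicity is a non-event in both (24.0% and 24.0%). This stands in full. The crude rate lies below the net risk of 30%, but that is a different quantity.
- **Toxicity stoppers.** A reader might infer that the plan removes them from the toxicity rates. The documents do not say so. The exclusion is worded for the primary endpoint only, and the intention-to-treat sentence in Section 13.0 and the continued surveillance in Section 10.2.1 point the other way. Section 13.0 also lets patients who cannot receive doxorubicin because of its toxicity stay on study for IMRT, which may keep the replaced group small. What stands is a conflict between sections, not a proven exclusion.
- **Size.** The part based on the documents' own figures is 1 to 2 points at R = 30%; anything larger needs an assumed loss rate. Deaths, losses and loco-regional progressions all count as primary failures, so a trial that meets its rule has at most 5 such patients among its 19 (26%). The illustration has more attrition than that, since 19 - 12.7 = 6.3 deaths alone exceed 5. The exact 95% interval for 4/19 runs from 6.1% to 45.6%. All true, but a wide interval does not correct a systematic error.
- **Timing and role.** The late window opens at 3 to 4 months and visits with grading are roughly three-monthly, so early onset would shrink the bias. Late toxicity carries no decision rule, and late dysphagia is also measured by swallowing studies to 24 months. These points limit the consequence. They do not supply a time point, a rule for lost patients or a denominator.

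**Conclusion.** The point holds in a limited form. Followed as written with 19 as denominator, the plan counts patients who are lost, or whose grading ends at progression, as free of late toxicity. For an assumed 30% net two-year risk that means 21.9% to 23.1% in place of 24.0%, or 19.7% with a further assumed loss of 10% a year. These figures rest on constant, independent hazards, on late onset spread over months 4 to 24, and on progression ending toxicity grading, which the documents neither state nor exclude.

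It would be too strong to say that late toxicity is certainly understated. The denominator is not stated, and one restricted to assessable patients could overstate it.

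Replacement of toxicity stoppers is a separate threat, chiefly to the acute rate. Its size depends on how many patients are replaced and whether they had the event. Sections 10.2.1, 13.0 and 14.0 do not settle whether they count and must be reconciled. This should be corrected, because describing toxicity prospectively is a declared purpose of the protocol; it does not affect the primary decision rule.

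**What to change.** In Section 14.0:
- Define the toxicity population as every patient who started chemoradiation, including those who stopped for toxicity and were replaced. Keep the 8 patients treated with IMRT alone as the separate summary already planned.
- Reconcile the reference to 19 patients with the intention-to-treat sentence in Section 13.0 and the surveillance provision in Section 10.2.1.
- Keep sample proportions with confidence intervals for acute toxicity.
- Report late toxicity as a cumulative incidence at 12 and 24 months, with death as a competing event, loss to follow-up censored and numbers at risk shown. The section already plans this type of analysis for loco-regional failure.
- State whether toxicity data collected after progression enter the analysis.

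The cost is some SAP wording and a little more analysis. Reported rates may be slightly less favourable. Intervals will stay wide with about 19 patients, and censoring at loss still assumes that loss is unrelated to toxicity.
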